8.1.1 Pharmacokinetic Analysis

Frozen plasma samples will be shipped on dry ice in batches to the laboratory of [name] at the University of Florida in Gainesville for PK analyses

The main PK objective is:

To assess imatinib PK and the relationship between PK and PD effects (immunologic and bacillary killing in WBA).

Within this main PK objective, specific PK analyses will aim to:

1. Identify pharmacokinetic parameter estimates, and concentration-time profiles of imatinib doses of 50, 100, 200, and 400 mg in healthy volunteers. Imatinib PK data was already obtained for 12 participants at the 50mg dose, and 4 at the 100mg dose in the previous version of the protocol.
2. Identify the pharmacokinetic/pharmacodynamic exposure-effect relationship between imatinib AUC or peak or trough and i) the change in the numbers of myelomonocytic cells in the blood between baseline and days 14 of therapy and ii) WBA.

We will first evaluate the robustness of our sampling strategy. The percentage of imatinib concentrations measured that are below the limits of quantification in any of the participants at any of the time points identified by D-optimality will be calculated. A result of 0% indicates that the optimal sampling strategy derived from sampling theory was likely to be optimal. Next, we will analyze all imatinib concentrations using ADAPT software of D'Argenio *et al* utilizing a compartmental PK analysis approach (41, 42). ADAPT software was developed using NIH funding, is open source, and has validated performance metrics, ensuring accuracy and robustness of findings from this software. We do not assume *a priori* how many compartments the imatinib PK model has; indeed some studies have described it as a one compartment model drug while others have found it is a two compartment model drug (8, 13, 43). We will examine one-, two-, and three-compartment models with first-order input and elimination. Estimation of

PK parameters will be based on the MLEM algorithm in ADAPT, as described above. The best number of compartments will then be chosen by comparing Akaike's information criteria, Bayesian information criteria, and -2 negative log likelihood scores for each model; we also apply the rules of parsimony. Goodness of fit is evaluated by examining the predicted/observed plots prior to- and after- the Bayesian step. Potential problems by concentration are sought by examining run-of-sine plots. Measures of Bias (mean error and weighted mean error) will be examined, as well as measures of Precision (mean squared error, weighted mean squared error, Bias-adjusted mean squared error and Bias-adjusted mean weighted squared error). The mean pharmacokinetic parameters, mainly volume of central compartment and clearance will be calculated for each participant, and utilized to calculate the half-life, peak concentration, the 0-24h area under the concentration-time curve (AUC₀₋₂₄/MIC) and the percentage of time that concentration persists in either the concentration zone associated with autophagy or myelopoiesis for each participant. Urine will be collected, frozen and stored for possible assessment of drug metabolites at the time of the PK studies.

The differences in clearance and volume (hence AUC and peak concentration) will be driven by the interindividual variability (IIV) and doses given. There will be 12 participants for each imatinib dose group who complete the PK studies (evaluable for PK data). With a population of 12 per group, for 4 dose groups, the power in detecting a 25% difference in clearance (which drives the AUC), given the IIV, is 90%.

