1.2.2.1 Human Pharmacokinetics

Human population PK of imatinib have been identified by Scmidli et al in 371 patients and are also a one compartment model: clearance of 14 L/hr with an inter-individual variability (IIV) of 32% and a volume of 252 L (13). These data are also consistent with population PK data from Widmer et al using data from 59 patients with CML or GIST (8).

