After assignment to a group, each participant will be assessed for baseline data according to [Table 1](#) prior to their first imatinib dose. They will then take their first imatinib dose. Participants will then come back at various times during the 14-day period of imatinib-only dosing (see [Section 6](#) on Study Procedures). During this time, safety assessments will be performed and blood will be collected for lab assays. Participants will be given imatinib in pre-filled pill containers at study visits indicated in the schedule of events. There will also be an intensive PK study performed on day 14. On this day, participants will have an IV placed to minimize discomfort related to phlebotomy at repeated time-points after dosing. Participants will return to complete the last PK blood draw on day 15 and will then continue taking imatinib at the same dose with addition of isoniazid 300 mg and rifabutin 300 mg orally per day for the subsequent 14 days. Study visits will include safety and efficacy assessments. In addition, we will conduct a PK study on day 28, with the final PK blood draw on day 29. Volunteers will then discontinue all study drugs and will complete one additional follow-up visit at day 42, 14 days after receiving their last dose, for safety. This will conclude data collection for Cohort 1.

Cohort 2: Enrollment in Cohort 2 will occur after the PK, PD, and safety data from Cohort 1 has been reviewed and two imatinib doses have been selected for further evaluation. The screening and intervention phase for Cohort 1 is the same as for Cohort 2 in terms of data collection. However, participants in Cohort 2 will begin taking rifabutin 300 mg per day and isoniazid 300 mg per day for 14 days followed by these drugs in combination with one of two selected doses of imatinib for an additional 14 days. Volunteers will be randomized to one of the two different imatinib dose levels. PK studies and the final study visit at day 42 will be completed as for Cohort 1. The primary and secondary objectives for Cohort 2 requires evaluable myelopoiesis and PK study data through day 28 from 12 participants in both of the imatinib dose groups (total 24 participants in Cohort 2, see [Section 8.1](#) and [Section 8.2](#)).

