Meal Timing for all participants in Cohorts 1 and 2: We will instruct participants to take drugs on an empty stomach in order to avoid the attenuation of INH absorption and potential for masking toxicity associated with higher drug levels when INH is taken with food. While taking imatinib without food may reduce drug levels, we want to describe a drug administration program that can be transferred to TB-infected patients in Africa, who are commonly instructed to take their anti-TB drugs after fasting. Our hypothesis is that low levels of imatinib will be associated with the optimal myelopoietic effect. If fasting reduces imatinib absorption and

imatinib drug levels, the recommended imatinib dose (from participants instructed to take all drugs while fasting) that is associated with the optimal myelopoietic effect may be higher than if imatinib were taken with a meal (i.e., 200 mg in fasting participants rather than 100 mg in participants who take the drug with a meal). In contrast, taking INH with a meal during this dose-finding study may reduce INH levels and could lead to an erroneous conclusion that the recommended dose of 600 mg INH in combination with imatinib is safe, when “real-world” consumption of the same INH dose in combination with imatinib while fasting could lead to INH toxicity. Thus we prefer to design a drug administration schedule in which participant safety is paramount. For the purposes of this study, all 3 drugs should be taken upon waking, within a 5-minute timeframe. Imatinib, then INH, then rifabutin. Breakfast may be eaten 1 hour after taking the study drugs. On study visit days, participants may eat a small breakfast at home at least 2 hours before the scheduled time of study drug administration (e.g. 7am), anticipating that the study drugs will be administered at the GCRC at 9am. On the PK study days (visits 4 and 8), a meal or snack will be provided 1 hour after study drug administration at the GCRC.

3.1.3 *Follow Up Phase*

Participants will be followed for an additional 14 days after study drug administration. All participation in the study should be complete by day 50 after enrollment.

3.1.4 *Allocation to Interventional Group*

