The precision in identifying both clearance and volume with PK sampling times we have chosen will be $>95\%$, which means very little bias and error. The differences in clearance and volume (hence AUC and peak concentration) will therefore be driven by the interindividual variability (IIV) and doses given. There will be 12 participants for each imatinib dose group in Cohort 1 who complete the PK studies (evaluable for PK data). With a population of 12 per group, for 4 dose groups, the power in detecting a 25% difference in clearance (which drives the AUC), given the IIV, is 90% for the first cohort study. In Cohort 2, which has 2 dose groups of 12 participants each (total=24), given the IIV% of clearances (rifabutin, isoniazid and imatinib), the power would be greater than 90% to detect a 25% change in TB drug clearance (hence AUC) for the 24 patients comparing results before and after addition of imatinib.

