1.2.2.1 Human Pharmacokinetics

Human population PK of imatinib have been identified by Scmidli et al in 371 patients and are also a one compartment model: clearance of 14 L/hr with an inter-individual variability (IIV) of 32% and a volume of 252 L (13). These data are also consistent with population PK data from Widmer et al using data from 59 patients with CML or GIST (8).

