After assignment to a group, each participant will be assessed for baseline data according to [Table 1](#) prior to their first imatinib dose. They will then take their first imatinib dose. Participants will then come back at various times during the 28-day period of imatinib-only dosing (see [Section 6](#) on Study Procedures). During this time, safety assessments will be performed and blood will be collected for lab assays. Participants will be given imatinib in pre-filled pill containers at visit 1 (day 1) as indicated on the schedule of events. There will also be an intensive PK study performed on day 14. On this day, participants will have an IV placed to minimize discomfort related to phlebotomy at repeated time-points after dosing. Participants will return to complete the last PK blood draw on day 15. Additional visits at days 21 and 28 will include safety and efficacy assessments. Volunteers will then discontinue all study drug and will complete one additional follow-up visit at day 42, 14 days after receiving their last dose, for safety.

Meal Timing for all participants: We will instruct participants to take drugs on an empty stomach. Our data on the first 16 participants dosed at 50 and 100mg of imatinib indicate that this results in expected PK exposures and is consistent with care of TB-infected patients, who are commonly instructed to take their anti-TB drugs after fasting. Breakfast may be eaten 1 hour after taking the study drugs. On study visit days, participants may eat a small breakfast at home at least 2 hours before the scheduled time of study drug administration (e.g. 7am), anticipating that the study drugs will be administered at the GCRC at 9am. On the PK study day (visit 4), a meal or snack will be provided 1 hour after study drug administration at the GCRC.

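### Version 5.0 claims 90% power for a 25% clearance difference with 12 per dose group; at the only documented IIV (32%) a comparison of two doses has about 45%

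*Combined protocol and SAP*

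**What the plan says.** Version 5.0, Section 8.1.1, expects 12 participants in each of four imatinib dose groups to complete the PK study. It then states that "the power in detecting a 25% difference in clearance (which drives the AUC), given the IIV, is 90" per cent. No IIV value is attached, and no contrast, test, alpha, sidedness or scale is given.

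The one numerical IIV for clearance is in the background, Section 1.2.2.1 of both protocol versions: "clearance of 14 L/hr with an inter-individual variability (IIV) of 32% and a volume of 252 L". It comes from a cited study of 371 patients.

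Version 3.0, Section 8.1.1, makes the same claim for Cohort 1: "given the IIV, is 90% for the first cohort study". Its companion figure for Cohort 2 is explicitly a before-after comparison, "for the 24 patients comparing results before and after addition of imatinib". Version 3.0 had two PK occasions, on days 14 and 28 (Section 3.1.2: "On the PK study days (visits 4 and 8), a meal or snack will be provided 1 hour after study drug administration"). Version 5.0 has one, on days 14 to 15 (Section 3.1.2 and Table 1: "On the PK study day (visit 4), a meal or snack will be provided 1 hour after study drug administration").

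**The concern.** The sentence describes a comparison among dose groups of 12, and each person receives a single imatinib dose. Differences between doses are therefore subject to the full between-person variability. With an IIV of 32% and 12 per group, a 25% difference is less than one standard deviation, which is too small for 90% power.

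A reader who trusts the figure would overestimate how well the trial can show whether clearance differs by dose. A non-significant comparison could be read as evidence that clearance does not change with dose, when a true 25% difference would be missed more often than not.

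**Working it through.** **Inputs.** n = 12 per group, four groups, all PK completers, so no dropout allowance (Version 5.0, Section 8.1.1). Difference 25%. IIV 32% (Section 1.2.2.1); its use for healthy volunteers is an assumption. Alpha is not stated; 5% two-sided is assumed, with one-sided also tried.

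**Attempt to reproduce the 90%: two doses, 12 v 12.** Noncentral t, df = 22, noncentrality = d × √(12/2) = d × √6. On the raw scale d = 0.25/0.32 = 0.781, so the noncentrality is 1.914. On the log scale the SD is 0.32 or √ln(1 + 0.32²) = 0.312.

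| Scale and direction | d | Two-sided 5% | One-sided 5% |
|---|---|---|---|
| Raw | 0.781 | 45% | 58% |
| Log, ratio 1.25 | 0.697–0.715 | 37–39% | 50–52% |
| Log, ratio 0.75 | 0.899–0.921 | 56–58% | 69–71% |

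Raw-scale versions with constant CV in both groups give 37% (increase) and 54% (decrease) two-sided. None of these reaches 90%.

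**Other between-dose comparisons at 32%.**
- Pairwise with error pooled over four groups (df 44), two-sided: 46% raw, 39–60% log.
- Four-group ANOVA with a 25% range between lowest and highest mean: 25–73%, depending on pattern and scale.
- Linear trend with a 25% total difference, two-sided: 42–64%.
- One dose against the other three (12 v 36): 54–77% two-sided, at most 86% one-sided.

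**What 90% would need (12 v 12, two-sided, raw).** The required d is 1.385. The IIV would have to be 25%/1.385 = 18.0%. At an IIV of 32% the detectable difference is 1.385 × 32% = 44.3%. For a 25% difference at 32%, about 36 per group would be needed.

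**Sensitivity to the assumed IIV (12 v 12, two-sided, raw).**

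| IIV | 18% | 20% | 25% | 32% | 40% |
|---|---|---|---|---|---|
| Power | 90% | 83% | 65% | 45% | 31% |

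**Expected precision at 32%.** The 95% CI half-width for a difference between two doses is 2.074 × 0.32 × √(2/12) = 0.271, or 27% of the mean. On 14 L/hr that is 3.8 L/hr, against a 25% difference of 3.5 L/hr.

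**Designs that do reach about 90% at 32%.**
- Paired test on 12, two-sided, raw, SD of the difference = 0.32 × √(2(1 − r)): 69% at r = 0.5, 79% at 0.6, 89% at 0.7, 97% at 0.8. The correlations are assumed; the documents give none.
- Paired test on 48: 91–99% even at r = 0.
- One-sample test against a fixed value: on 12, one-sided, for a decrease, 89–91%; on 48, above 99%.
- Two doses against two (24 v 24), one-sided, for a decrease, constant CV or log scale: 92–93%.
- Trend with 25% per dose step, a far larger total difference: above 99%.

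**The case against.** The strongest reply is that the plan never names a comparison of two doses. The 45% belongs to a contrast chosen here, and several designs reach 90% with the same IIV. The 32% is a background value from patients; the plan does not tie the power sentence to it, and healthy volunteers selected under narrow criteria may vary less. The planned analysis is compartmental modelling, not a t-test, and power under that model was not computed. Finally, little depends on the sentence.

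Parts of this stand. Because the basis is unstated, the 90% cannot be shown to be a slip in a known calculation. The IIV is an assumption, which is why a range is shown. The limited impact is real.

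The rest does not rescue the figure. The wording, 12 per group in four dose groups, points to a comparison between groups, and no two-sided comparison tried for a 25% difference between doses reaches 90% at 32%. A paired contrast is not available to the 32 participants enrolled under Version 5.0, who have one PK occasion. A one-sample test needs a reference value that the section does not give. Modelling does not remove between-person variability; pooling the variance over all four groups lifts 45% only to about 46%.

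An origin in a within-person calculation is possible, since Version 3.0 had two PK occasions. Against it, Version 3.0 reserves before-after wording for Cohort 2. This cannot be settled from the documents.

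**Conclusion.** The concern holds. The 90% has no stated basis and is not reproduced for a between-dose comparison at the documented IIV. For two doses of 12 the power is about 45% on the raw scale (37–58% over scale and direction, two-sided 5%; at most 71% one-sided). This rests on an IIV of 32% carrying over from patients to healthy volunteers and on a between-dose reading of the sentence. An IIV near 18% would give 90%, but the documents offer no such value.

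The consequence is limited. PK is a secondary objective, and the aims listed in Section 8.1.1 are parameter estimation and exposure-effect. The sample size, escalation rules and exposure-effect analysis do not depend on this figure. It should be corrected because, as written, it overstates what the PK data can show about clearance by dose.

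**What to change.** Replace the sentence in Version 5.0, Section 8.1.1, in one of three ways.

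1. Restate it with its contrast, test, alpha, scale and IIV. For example: at an IIV of 32%, with 12 per dose group and a two-sided 5% two-sample t-test on the raw scale, power for a 25% difference in clearance between two doses is about 45%, and the difference detectable with 90% power is about 44%.
2. State and justify an IIV and a test that give 90%. The 16 participants who already have imatinib PK data (12 at 50 mg, 4 at 100 mg) could supply a study-specific IIV.
3. Delete the power claim.

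In each case report clearance by dose as estimates with 95% confidence intervals.

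The cost is wording only, with no added participants, visits or samples. The stated figure becomes less favourable, gains a basis, or is removed.

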8.1.1.1. Drug-drug pharmacokinetic interactions

* While DDIs between imatinib, isoniazid, and rifabutin are no longer a focus of the study, the following language has been left in the protocol as these associations may be analyzed in participants enrolled in the previous protocol in the 50 and 100mg arms. We have recently introduced machine learning or artificial intelligence (AI) based algorithms to pharmacometrics to identify PK covariates, including genotypic, demographic, clinical, laboratory features, and concomitant medications (44, 45). We will examine the effect of rifabutin and isoniazid PK parameters, demographic features, laboratory values, and RNA-seq signatures, in each participant, on imatinib PK parameters and variability, and hence identify the DDIs if present. We will compare baseline pre-treatment blood samples with those taken after imatinib alone or after imatinib plus isoniazid and rifabutin. This will be performed using Salford Miner software.

Moreover, algorithms such as MARS give a final output equation of the covariates which can be directly used to identify the optimal dose for use in the case that DDI are identified.

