1.9 Protocol Review, Finalization, and Approval Processes

The protocol will undergo a review, approval and set-up phase with the Georgia CTSA GCRC during the first 2 months of funding, as well as the Protocol Registration process with NIAID/DAIDS. A protocol-specific Manual of Operational Procedures in accordance with NIAID/DAIDS requirements will also be prepared and approved during this timeframe, incorporating procedures needed for this study and existing SOPs from the Winship CTO, Georgia CTSA GCRC and Core Lab, IDS Pharmacy, and Emory University Medical Laboratory.

2 Study Objectives

The overall objective of the study is to determine safe and immunologically effective doses of imatinib that will subsequently be advanced to a phase 2 randomized clinical trial in adults with drug-susceptible pulmonary TB. Because of possible drug-drug interactions with isoniazid and rifabutin, we also aim to evaluate safety issues with eventual use in patients with TB taking TB drugs. These issues concern both effects of imatinib on TB drug levels as well as effects of TB drugs on imatinib levels. For example, imatinib's tendency to inhibit CYP3A4 could increase rifabutin levels and the risk of dose-dependent rifabutin toxicity. Rifabutin induction of CYP3A4

could in turn decrease imatinib exposure, as explained above. In addition, the time courses of CYP enzyme inhibition or induction in humans taking imatinib and in those taking rifabutin and isoniazid are uncertain.

Thus, the dosing schedules and rationale are as follows: in Cohort 1, we will give imatinib alone for 14 days – which is required to observe an effect of imatinib on myelopoiesis (the primary endpoint), followed by imatinib in combination with rifabutin and isoniazid for an additional 14 days. This should give imatinib sufficient time to inhibit CYP3A4, which could lead to high rifabutin levels, during the 28-day course of drug dosing in Cohort 1. However, in the clinical trial that will occur subsequent to this study, patients will be diagnosed with TB in the community, where they may be promptly started on TB drugs, and then if enrolled they will subsequently have imatinib added to these drugs. Thus, in Cohort 2 we will give TB drugs first for 14 days in order to reach steady state, followed by imatinib in combination with rifabutin and isoniazid for an additional 14 days. This should provide for sufficient time to examine how rifabutin's induction of CYP3A4 affects imatinib levels.

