Imatinib is well tolerated in CML patients, and a maximal tolerated dose has not been defined, but >800mg/day is rarely used. Most adverse effects, even at the highest doses, are grade 1 (mild) or grade 2 (moderate). Most patients have a reduction in the Hgb level of 1 to 2 mg/dL; the hemoglobin level typically increased to base-line values or higher with continued therapy. Drug induced anemia during long-term administration has been rarely seen. Neutropenia occurs in chronic phase CML patients treated with imatinib at the onset of blast crisis, but is unlikely to occur in patients receiving low doses in the absence of hematological disease. Inhibition of normal hematopoiesis does not occur in Philadelphia chromosome negative patients, although further clinical assessment will be required to ensure this. Imatinib is an inhibitor of CYP2C9, CYP2D6 and CYP3A4. Thus, drugs metabolized through these enzymes, including rifabutin, in some patients could require alterations in dosing and/or dose interval. In the PK studies proposed, being on these drugs with major CYP enzyme interactions will serve as exclusion criteria. We will also monitor QT intervals with ECGs for all study participants. In summary, we expect these doses of imatinib to be very safe. Isoniazid and rifabutin are also medications with a well-known safety profiles. Toxicity may be idiosyncratic or dose-dependent. Because we are administering these drugs over only 14 to 28 days in healthy participants, we expect tolerability to be high.

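### The optional interaction analysis in Version 5.0 section 8.1.1.1 does not state the within-person day 28 to day 14 imatinib comparison, and the covariate analysis it does state can mislead depending on which records enter

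*Combined protocol and SAP*

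**What the plan says.** Version 5.0 section 8.1.1.1 says that interactions between imatinib, isoniazid and rifabutin are no longer a focus, but keeps the method because "these associations may be analyzed in participants enrolled in the previous protocol in the 50 and 100mg arms". The method is: "We will examine the effect of rifabutin and isoniazid PK parameters, demographic features, laboratory values, and RNA-seq signatures, in each participant". The outcome is each person's imatinib PK, and any interaction is read from these covariate effects. The only comparison between periods is: "We will compare baseline pre-treatment blood samples with those taken after imatinib alone or after imatinib plus isoniazid and rifabutin". The section adds that the MARS output equation "can be directly used to identify the optimal dose for use in the case that DDI are identified".

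The data come from Version 3.0. Under section 3.1.2 of that version, each Cohort 1 participant took imatinib alone to day 14, then imatinib with rifabutin 300 mg and isoniazid 300 mg daily to day 28, with PK profiles scheduled on days 14 and 28. Version 5.0 section 8.1.1 reports imatinib PK for 12 participants at 50 mg and 4 at 100 mg, so there are at most 16 pairs. The PK aims in Version 3.0 section 8.1.1 included testing whether the standard rifabutin and isoniazid doses are covariates of imatinib clearance. The Version 5.0 aims do not.

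**The concern.** With fixed rifabutin and isoniazid doses, differences in rifabutin exposure between people reflect their own disposition and adherence. They do not reflect assigned dose. Version 5.0 section 1.2 describes imatinib as both a CYP3A4 substrate and an inhibitor. Version 3.0 section 12.1 lists enzymes that imatinib inhibits, CYP3A4 among them, and refers to "drugs metabolized through these enzymes, including rifabutin". Version 3.0 section 2 adds that "imatinib's tendency to inhibit CYP3A4 could increase rifabutin levels and the risk of dose-dependent rifabutin toxicity".

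A person with low enzyme activity can therefore run high on both drugs, and imatinib may itself raise rifabutin. Either route produces a positive association between rifabutin and imatinib exposure across people, even if adding rifabutin lowers imatinib exposure in every one of them. Cohort 1 had no rifabutin period without imatinib to separate these routes. A slope taken across people could thus report an interaction in the wrong direction, while the same participants' paired profiles would show it directly.

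**Working it through.** **No figure to reproduce.** Section 8.1.1.1 states no sample size, power or error rate. The nearest PK figure, 90% power for a 25% clearance difference (Version 5.0 section 8.1.1), is framed by dose groups. Nothing below depends on it.

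**Inputs from the documents**
- At most 16 pairs: 12 at 50 mg and 4 at 100 mg.
- Between-person variability of imatinib clearance 32% (section 1.2.2.1), so log-scale SD = sqrt(ln(1 + 0.32²)) = 0.312.

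**Assumed, because the documents give no value**
- True day 28/day 14 imatinib AUC ratio 0.75 in everyone.
- Rifabutin between-person variability also about 32%.
- Cross-drug correlation rho of 0, 0.3, 0.5 or 0.7.
- Within-person log SD 0.15.

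**Model.** For person i, log A14 = u + e1 and log A28 = u + ln(0.75) + e2, where u has SD 0.312 and is correlated rho with log rifabutin AUC. The expected slope of log A28 on log rifabutin AUC is rho × (SD of u)/(SD of log rifabutin), which is about rho. The term ln(0.75) is common to everyone, so it moves only the intercept. The slope therefore carries no information about the fall. A positive slope counts as the wrong sign. Ordinary least squares stands in for MARS.

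**Results, n = 16, 20,000 runs each**

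| rho | Slope positive, day 28 only | Significantly positive (two-sided 5%) | Wrong sign, both days stacked | Wrong sign, paired ratio |
|---|---|---|---|---|
| 0 | about 50% | about 3% | 0% | 0.0% |
| 0.3 | about 85% | 16 to 18% | under 1% | 0.0% |
| 0.5 | about 96% | about 44% | about 1% | 0.0% |
| 0.7 | 99.7% | about 79% | 3 to 4% | 0.0% |

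The stacked fit uses both days, with rifabutin AUC set to zero on day 14. The paired ratio recovers 0.75 throughout.

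**Sensitivity.** Suppose induction also strengthens with rifabutin exposure, with an assumed log-log slope of -0.29. The expected slope becomes about rho - 0.29, and the day-28-only fit has the wrong sign in about 16, 50, 78 and 96% of runs. With n = 12 and no such dependence, the figures are about 50, 82, 94 and 99%.

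**Precision of the paired ratio.** The 90% CI multiplies and divides the ratio by exp(h), where h = t(0.95, n-1) × s_w × sqrt(2/n) and s_w = sqrt(ln(1 + CV²)). CV is the assumed within-person value.
- n = 16, CV 15%: 1.753 × 0.149 × 0.354 = 0.092, factor 1.10.
- n = 16, CV 30%: 1.753 × 0.294 × 0.354 = 0.182, factor 1.20.
- n = 12, CV 15%: 1.796 × 0.149 × 0.408 = 0.109, factor 1.12.
- n = 12, CV 30%: 1.796 × 0.294 × 0.408 = 0.215, factor 1.24.

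In the widest case an observed ratio of 0.75 has an upper limit of 0.75 × 1.24 = 0.93, which still excludes 1.

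**The case against.** The strongest reply is that section 8.1.1.1 never says the fit uses day-28 records alone. It mentions samples from both periods and names concomitant medications as a type of covariate, and section 8.1.1 says all imatinib concentrations will be analysed. A fit with both days, or with a term for co-administration, largely avoids the problem. This stands. The wrong-sign rates are conditional on a choice the plan leaves open.

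Other points also stand:
- A wrong-signed estimate is not a wrong conclusion. The significant-error rates are lower, about 3% at zero correlation.
- The documents do not establish net induction. Version 3.0 section 1.4 says the combined effect of isoniazid and rifabutin is unknown and may offset.
- Version 3.0 says only that imatinib could raise rifabutin levels, not that it does.
- A reader might infer that the baseline comparison is a faulty exposure contrast, because pre-treatment blood holds no imatinib. The sentence follows the mention of laboratory values and RNA-seq, and the Version 3.0 schedule draws RNA blood on days 1, 14 and 28 but PK blood only around days 14 and 28. It more plausibly concerns those covariates.
- The analysis is optional and absent from the Version 5.0 objectives and endpoints, whose imatinib doses are already set.

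None of this supplies the missing comparison. Version 5.0 does not state the paired imatinib contrast, and the earlier aim that could have carried it is gone.

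**Conclusion.** The point holds at low severity. Section 8.1.1.1 infers an interaction from covariate effects, leaves open which records enter, and omits the within-person comparison that the scheduled profiles allow. If day-28 records alone were used, the sign of the slope would be unreliable: a coin toss at zero cross-drug correlation and usually wrong at 0.3 or above, given a true ratio of 0.75. If both days were used, the risk would be 0 to 4%. These figures rest on the assumed correlation, effect, rifabutin variability and within-person SD, and on a one-predictor linear fit in place of MARS.

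Two stronger readings are not supported. One is that the planned analysis will give the wrong sign; the text does not fix the model that would do so. The other is that the paired data could explain the combination toxicity behind the amendment. That toxicity was at 100 mg, where only 4 participants were carried over, and Version 3.0 section 9.5 says that those taken off drug do not take part in PK studies. The estimate will rest mainly on the 50 mg arm.

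**What to change.** In Version 5.0 section 8.1.1.1:
- Define the interaction estimate as the within-person geometric mean ratio (day 28/day 14) of imatinib AUC0-24, peak and clearance, with 90% CI, in carried-over participants with both profiles.
- Report the number of pairs by dose and the reasons for missing day-28 profiles.
- Keep MARS as exploratory, state which records enter it, and remove the statement that its equation can be "directly used to identify the optimal dose for use in the case that DDI are identified".
- State the limits: order is confounded with time on imatinib; the ratio is the joint effect of rifabutin and isoniazid; and participants taken off drug for toxicity have no day-28 profile.

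The cost is one paragraph. No new samples are needed, because the profiles were scheduled under Version 3.0.
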